The Effect Of Sacral Massage On Labour Pain and Anxiety: A Randomized Controlled Trial

Objective: This study was conducted as a randomized, control experimental study to determine the effect of sacral massage, on labour pain and anxiety.

Background

Labour is regarded as one of the physiological behaviours in humans that has existed since the beginning of humanity, the formation cycle of which has remained unchanged (Gönenç & Terzioğlu, 2012). Labour is a health state that most women aspire to, at some point in their lives. The first thought that comes to the mind of an expecting woman regarding her delivery is the pain of labour. The pain of the labour is the central and universal part of woman's experience of childbirth. Labour is a normal physiological process, which while should be an occasion for rejoicing, it also accompanies with it, lots of pain, agony, and discomfort and certain risks. Thus although being a joyful and empowering experience it can end with negative and tragic results, leaving the woman filled with fear and anxiety for future birth (Labrecque, Nouwen, Bergeron, & Rancourt, 1999). The causes of labour pain can be either physical or psychological. Physical factors include uterine contractions, cervical dilatations, cervical effacements etc. Psychological factors include fear and anxiety, previous experiences, inadequate support, inadequate knowledge. Pain perceived during labour may be different for each woman (Sethi & Barnabas, 2017). The fear and anxiety that pregnant women experience during the labour process leads to the stretching of pelvic muscles and creates resistance against the repulsive force of the uterus and the repulsive force exerted by the women during labour. The extension of the anxiety-related tension in the pelvic muscles causes general fatigue in pregnant women, increased pain and decreased power to cope with the pain (Gönenç & Terzioğlu, 2012). Feelings of anxiety can cause pregnant women to inappropriately respond and lose their self-control. Anxiety also reduces the self-confidence of an individual. As a result of this situation, pregnant women perceive themselves as incompetent and unskilled. The anxiety experienced during labour directs women to caesarean section by their own will (Fenwick et al., 2010). The essence of midwifery can be with woman providing comfort in labour. Touch communicates caring and reassurance. Manual healing methods used today during delivery include touch and massage therapy. Painful uterine contractions can be treated by applications of pressure with the hands to woman's back, hips, thighs and sacrum. By massage therapy, pharmacological management during the first stage of labour can be reduced. So less negative effects will be

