The study was conducted with two groups, namely Massage Group (experimental), and Control Group. 30 pregnant women were included in each group; therefore, the study was conducted with a total of 60 pregnant women. The women who participated in the study were randomized randomly as control (double) and experimental (single) groups according to the single or double patient admission numbers. The women who participated in the study were randomized into either the control (double) or the experimental (single) group according to single or double patient admission numbers.

Measurements

In this study, the Questionnaire form, Birth action follow-up form, postpartum interview form ,Visual analogue scale (VAS) and State-trait anxiety inventory (STAI FORM TX-I) were used to collect the data.

1. *Questionnaire Form:* Questions that reflect the sociodemographic characteristics of the patients (age, educational status, social security, marital status), information about pregnancy (drugs used, status of their willingness to become pregnant, gestational week, status of attending examinations, status of collecting information about labour), the methods used to cope with the pain, and open-ended questions that evaluate the previous use of massage.

2. *Birth Action Follow-Up Form:* The questions that indicate the length of the first phase, the interventions performed to shorten the first phase of labour, the methods used by the patient to cope with the labour pain, the emotional behaviours of the pregnant women during labour, the length of the second phase, adjustment of the pregnant women, the presence of intervention in labour, the status of episiotomy, the total duration of labour and the baby's health.

3. *Postpartum Interview Form:* Open and closed questions that indicate the pregnant women's thoughts about labour, the status of overall satisfaction with labour and how the women feel were included in this form, which was prepared by a researcher in accordance with the relevant literature.

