4. *Visual Analogue Scale (VAS):* The Visual Analogue Scale (VAS) was used to measure the severity of labour pain. On this scale, numbers from 0 to 10 appear on a horizontal line of 100 mm. The pain level is expressed in figures that range from 0 to 10, as follows: the absence of pain is indicated by "0", while the most severe pain is indicated by "10". In this method, it is explained to the individual that there are two endpoints and that he/she is free to mark any point that defines his/her pain.

The VAS was applied to the participants in the control group once in the latent (3-4 cm), active (5-7 cm) and transition phases (8-10 cm) of labour. The VAS was also applied to those in the experimental group once after the massage in each phase. The diagnosis was made in accordance with the subjective data including the patient's verbal expression.

5. State-Trait Anxiety Inventory (STAI FORM TX-I): To determine state and trait anxiety levels of the participants, the state-trait anxiety inventory (STAI FORM TX -I) was used. The individual is required to indicate the feelings or behaviours that he/she has experienced in a specific situation according to the degree of severity by marking one of the options such as (1) Never, (2) Little, (3) Very and (4) Completely. The state-trait anxiety inventory requires the individual to describe how he/she feels at a certain moment and under certain conditions by considering his/her feelings about a specific situation. While high scores indicate high anxiety levels, low scores indicate low anxiety levels. The state-trait anxiety inventory consists of 20 statements. The score obtained from the scale may vary between 20 and 80. While a high score represents a high anxiety level, a low score represents a low anxiety level. In the scoring performed in accordance with the criteria directive, 0-19 points are regarded as "none", 20-39 points are regarded as "mild anxiety", 40-59 points are regarded as "moderate anxiety", 60-79 points are regarded as "heavy anxiety" and 80 points are regarded as "severe anxiety". In our study, the STAI FORM TX-I was used in the active (5-7 cm) phase in the control group and in the active (5-7 cm) phase after the massage in the experimental group to evaluate the anxiety experienced by women during labour.

Data Collection

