After approval and permission to conduct the study were obtained from the ethics committee, the hospital's head nurse, delivery room charge nurse/midwife and other midwives and nurses were interviewed and informed about the purpose and scope of the study. Data were collected by one of the researchers. The researcher was aware of which patients were assigned to each group. However, the researchers did not interfere in any way with the study results. When they encountered women who met the inclusion criteria of the study, the purpose of the study was explained, and written consents were received from those who agreed to participate in the study. For the women who satisfied the criteria, participation in the study was voluntary. Additionally, during the study, no women requested to withdraw and no women were excluded from the study. Routine care and treatments for the women continued during data collection.

Procedure

Before the research data were collected, an informative meeting regarding the purpose and scope of the study was held for the members of the healthcare team who worked in the obstetrics and gynaecology clinic of the Turkish Republic Ministry of Health Public Hospitals Administration of Turkey, at the Istanbul Province xxx Training and Research Hospital, where the study would be conducted. In addition, cooperation was provided by the members of the healthcare team. For the correct application of the massage, the researcher was trained by the physical therapist who work at hospital. The massage was applied only to the pregnant women in the intervention group at every phase of labour. There was no intervention in the control group except for routine hospital applications. The steps taken in this study are discussed below.

For the pregnant women included in the experimental group:

- One-on-one interviews were conducted with the pregnant women, and the voluntary disclosure forms, which explained the purpose of the study, were completed.
- The prepared questionnaire form was applied.

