- In addition to providing them with routine nursing/midwifery care, the women in the experimental group were administered a massage to the sacral region under the supervision of a doctor for 30 minutes using the effleurage (patting) (15 minutes) and vibration technique (15 minutes) in the latent (3-4 cm), active (5-7 cm) and transition (8-10 cm) phases of labour. To achieve this, the patients were placed in the left lateral position in the latent (3-4 cm), active (5-7 cm) and transition (8-10 cm) phases of labour.
- The state-trait anxiety inventory (STAI FORM TX-I) was applied and evaluated after the massage in the active (5-7 cm) phase.
- The Visual Analogue Scale (VAS) was evaluated once after the massage in the latent (3-4 cm), active (5-7 cm) and transition (8-10 cm) phases.
- Birth action follow-up form and postpartum interview forms were applied.

For the pregnant women included in the control group:

- One-on-one interviews were conducted with the pregnant women, and the voluntary disclosure forms, which explained the purpose of the study, were completed.
- The prepared questionnaire form was applied.

- Routine nursing/midwifery care was applied.
- The state-trait anxiety inventory (STAI FORM TX-I) was applied and evaluated in the active (5-7 cm) phase.
- The Visual Analogue Scale (VAS) was evaluated once in the latent (3-4 cm), active (5-7 cm) and transition (8-10 cm) phases.
- Birth action follow-up form and postpartum interview forms were applied

One-on-one interviews were conducted with the women in both groups, and the voluntary disclosure forms, which explained the purpose of the study, were completed. After the prepared questionnaire form was applied to the women in the experimental group, routine nursing/midwifery care was provided.

Hypotheses of the Study

1. Massage applied to the sacral region decreases the perception of a woman's labour pain.
2. Massage applied to the sacral region decreases the woman's levels of concern and anxiety about labour.
3. Massage applied to the sacral region increases the woman's satisfaction with the labour.

REFERENCES

Field, T. (2010). Pregnancy and labor massage. Expert Review of Obstetrics & Gynecology, 5(2):177–181.

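### VAS is read after a 30-minute massage in one arm and at an unspecified moment of the same dilatation band in the other, so the t-test cannot separate a massage effect from a possible difference in reading time

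*Protocol*

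**What the plan says.** The Protocol's Procedure section gives each arm its own reading rule.

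- Massage arm: women were "administered a massage to the sacral region under the supervision of a doctor for 30 minutes" in each of the three phases. For pain, "The Visual Analogue Scale (VAS) was evaluated once after the massage in the latent (3-4 cm), active (5-7 cm) and transition (8-10 cm) phases".
- Control arm: "The Visual Analogue Scale (VAS) was evaluated once in the latent (3-4 cm), active (5-7 cm) and transition (8-10 cm) phases". No time, dilatation or triggering event is attached.

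The Measurements section repeats the split. Item 4 says of pain: "The VAS was also applied to those in the experimental group once after the massage in each phase". Item 5 places the single STAI "in the active (5-7 cm) phase in the control group and in the active (5-7 cm) phase after the massage in the experimental group".

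Controls receive routine care only, with no equivalent 30-minute period. No VAS or STAI before the massage is described. Under Data Collection, one researcher gathers the data, and "The researcher was aware of which patients were assigned to each group". The woman marks the VAS herself, but the plan does not say who chooses the moment for a control reading.

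The Birth Action Follow-Up Form is described as containing "The questions that indicate the length of the first phase, the interventions performed to shorten the first phase of labour", among other items. Neither the time of a VAS reading nor the dilatation at it is listed. The SAP plans t-tests and chi-square tests, with no adjustment for either.

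**The concern.** A massage-arm reading cannot fall in the first 30 minutes of a band, because a 30-minute massage given in that band comes first. Nothing stops a control reading from falling there. The Protocol's own Background gives a reason why this could matter: "Physical factors include uterine contractions, cervical dilatations, cervical effacements etc". If pain rises with dilatation, a woman read later in a band may score higher for that reason alone.

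Pain score is the subject of the first hypothesis and a dependent variable in the SAP. A timing difference produced by the two reading rules arises after allocation, so even sound randomisation would not remove it. An unadjusted comparison of means would count it as part of the massage effect, either hiding a benefit or adding to one.

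**Working it through.** **The plan's own figure.** The Protocol gives 30 per group at alpha 0.05 and power 0.80, but no mean difference and no SD, so 30 can only be solved backwards. Two-sided (sidedness is not stated), the normal formula gives d = (1.960 + 0.842) × √(2/30) = 0.723. The t distribution with 58 degrees of freedom gives d = 0.736. This point does not dispute the sample size; d = 0.736 serves only as the effect with 80% power.

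**Inputs from the documents.** Massage length 0.5 h; 30 women per arm; nominal bands 3-4, 5-7 and 8-10 cm, so widths of 1, 2 and 2 cm.

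**Assumptions, none in the documents.** Dilatation rate r = 1 cm/h (0.5 and 2 also tried); pain slope 0.5 to 1.0 VAS points per cm; SD 2 points; and where in the band massages start and control readings fall. At SD 2, d = 0.736 is 0.736 × 2 = 1.47 points.

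**Case 1: readings spread evenly in both arms.** Measure position in cm from band entry, with band width W.

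- Control: even over 0 to W, mean W/2.
- Massage: even over 0.5r to W, mean (0.5r + W)/2.
- Control minus massage: W/2 − (0.5r + W)/2 = −0.25r, whatever the width, provided the massage fits in the band.

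At r = 1 the massage arm is read 0.25 cm later on average. The shift is 0.25 × 0.5 = 0.125 to 0.25 × 1.0 = 0.25 points against massage, or 0.0625 to 0.125 SD. The effect left to detect is 0.736 − 0.0625 = 0.673 to 0.736 − 0.125 = 0.611. By the noncentral t (noncentrality d × √15, df 58, two-sided 0.05):

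| r (cm/h) | Shift against massage (SD) | Power, from 80% |
|---|---|---|
| 0.5 | 0.031 to 0.0625 | 76.5% to 72.7% |
| 1 | 0.0625 to 0.125 | 72.7% to 64.3% |
| 2 | 0.125 to 0.25 | 64.3% to 45.6% |

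With no true effect at r = 1, false rejection in favour of massage falls from 2.5% to between 1.4% and 0.7%. A simulation at r = 1 and W = 2 cm (100,000 runs), which also carries the extra variance from spread in position, gives power of 72.3% and 61.8% at the two slopes.

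**Case 2: control read at band entry, massage started at entry.** The massage arm is read 0.5 cm later. The shift is 0.25 to 0.50 points against massage, and power is 64.3% to 45.6%.

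**Case 3: control read at mid-band, massage started at entry.** The shift is (W/2 − 0.5) × slope in favour of massage. In a 2 cm band it is 0.25 to 0.50 points (0.125 to 0.25 SD), and the two-sided 5% error becomes 7.6% to 15.9%. In a 1 cm band, the nominal latent width, it is zero.

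**The case against.** Several points against the concern have force.

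- **Shared bands.** Both arms are read within the same dilatation limits, which bounds the mismatch. This stands, but the bands do not fix position inside them.
- **Reading after the massage is sensible for an acute effect.** Agreed. What is missing is a corresponding moment for controls.
- **Silence is not a rule.** A reader might infer that control readings were scattered over the whole band. The Protocol does not say so; it names no moment. Readings may have been matched in practice, but the plan neither requires this nor lists a record that would show it.
- **Direction.** A reader might infer that the design favours massage. The documents do not support that. Under even reading the shift works against massage, and a false claim of benefit becomes less likely. Case 3 needs early massage together with later control readings, and nothing in the documents shows that pattern.
- **STAI.** A reader might extend the bias to anxiety because the wording is asymmetric in the same way. The documents link no anxiety score to time within the band, so neither direction nor size can be inferred.
- **Records.** The SAP lists phase durations as dependent variables, so phase start and end times must have been obtained in some form, and the form's contents are only summarised. This narrows the gap, but the time of each reading is still not listed.
- **Allocation known to the data collector, and no pre-massage reading.** These are separate matters. Neither shows a timing difference, and neither adds weight here.

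**Conclusion.** The point holds for the VAS. Followed as written, the plan permits a systematic difference in reading time between arms, and the planned t-test cannot separate that from a massage effect. No actual difference is claimed, because the documents give no reading times.

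Direction and size are unknown. The even-reading case gives 0.125 to 0.25 points against massage and power of about 73% to 64% in place of 80%. That rests wholly on the assumed 1 cm/h, 0.5 to 1.0 points per cm and SD of 2. For the STAI, only the asymmetry of wording can be stated.

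This should be corrected, with medium confidence: the two reading rules are plain in the text, but their consequence cannot be measured from it.

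**What to change.** In Measurements (items 4 and 5) and Procedure, define t0 as the examination that first places the woman in the band. Start the massage at t0. In both arms, take the VAS at t0 + 30 to 35 minutes, and the active-phase STAI at the same point. Keep the phase bands. If a routine examination shows that the woman has left the band before the reading, still take it, flag it, and show results with and without flagged readings. Record t0, reading time and last routine dilatation on the Birth Action Follow-Up Form, and report them by arm and phase.

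The cost is new wording in two sections and two or three form fields, with no extra examination. There is a scheduling burden, since the single researcher may be massaging one woman when another's reading falls due. The match is also imperfect: t0 depends on how often women are examined, and equal elapsed time does not guarantee equal dilatation, which is why dilatation should be reported too.

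The Protocol describes a study already conducted, in 2016. For those data, report reading times and dilatation by arm where recorded. Otherwise state as a limitation that the arm difference in VAS cannot be separated from reading time.

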Data analysis

In the evaluation of the data, in addition to descriptive statistical methods (e.g., percentage, frequency, mean, and standard deviation), the chi-square test and Student's t-test were used in the comparison of the qualitative data. The results were evaluated at a significance level of $p < 0.05$.

The dependent variables of the study are the pain score averages of the pregnant women, the duration of the latent, active and transition phases of labour, and the anxiety level score. The independent variables of the study are the pregnant women's age, educational status, working status, and prenatal educational status, as well as the educational status of the husbands of the pregnant women, their willingness to become pregnant and the willingness to serve as controls before labour.

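### The SAP names background factors as independent variables but plans only one-factor tests, so the massage effect is never estimated with those factors held equal

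*SAP*

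**What the plan says.** The whole analysis plan is the SAP section Data analysis. Besides descriptive statistics, it states that "the chi-square test and Student's t-test were used in the comparison of the qualitative data", with results judged at p < 0.05. The outcomes are pain scores, the durations of the three labour phases and the anxiety score. On the explanatory side it states: "The independent variables of the study are the pregnant women's age, educational status, working status, and prenatal educational status". The list goes on to the husband's education, willingness to become pregnant and one further item, seven in all. Allocated group is not on it. No regression, analysis of covariance or stratified analysis appears in either document.

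In the Protocol, under Measurements, the Questionnaire Form covers "Questions that reflect the sociodemographic characteristics of the patients (age, educational status, social security, marital status), information about pregnancy". The pregnancy items include willingness to become pregnant and whether the woman had collected information about labour. Under Procedure, the form is listed before the massage in the experimental group and before routine care and outcome measurement in the control group.

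The arms are formed by putting women with odd numbers in the "experimental (single) group according to single or double patient admission numbers", 30 per arm. All three hypotheses concern massage; none concerns age, education or another background factor.

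**The concern.** A t-test or a two-way chi-square test handles one grouping factor at a time. Under this SAP it can compare the arms and ignore the background factors, or relate one background factor to an outcome and ignore the arms. The second use answers none of the hypotheses. Neither gives massage versus control among women alike in age, education and willingness to become pregnant. The SAP thus declares a set of variables that its own tests cannot bring to bear on the trial's question.

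Two things are at stake. First, nothing in the allocation method balances these factors, so if one differs between the arms and is related to pain or anxiety, the difference passes into the VAS and STAI comparison. Second, whatever outcome variation the factors explain stays in the error term of a trial fixed at 60 women. The remedy needs no new measurement, because the core factors are already on the Questionnaire Form.

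**Working it through.** **Which factors are documented in both places**

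| SAP independent variable | Questionnaire Form (Protocol) |
|---|---|
| Age | yes |
| Educational status | yes |
| Willingness to become pregnant | yes |
| Prenatal education | near match only (collecting information about labour) |
| Working status | not listed |
| Husband's education | not listed |
| Willingness to serve as controls before labour | meaning unclear; no clear match |

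Three factors are usable on the documents alone.

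**What 30 per arm detects.** The Protocol gives alpha 0.05, power 0.80 and 30 per group, but no effect size, SD or sidedness, so its sample size cannot be reproduced. It can only be solved backwards. With a two-sided t-test (assumed), 58 degrees of freedom and noncentrality d × √(30/2), 80% power requires d = 0.736 SD.

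**Chance imbalance under ideal randomisation.** Take two independent binomial counts out of 30. The probability that they differ by 6 women or more (20 points) is 14.7% at prevalence 40% and 15.5% at 50%. A two-sided 5% test detects a true 20-point imbalance only about 35% of the time, so a non-significant baseline comparison is weak reassurance.

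**Effect of such an imbalance.** Shift = factor effect × imbalance. The factor effect is an assumption; the documents give none.
- 0.5 × 0.20 = 0.10 SD; 0.10/0.736 = 14% of the detectable difference.
- 0.7 × 0.20 = 0.14 SD; 0.14/0.736 = 19%.

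**Conditional error rate.** Fix 18 versus 12 women with the factor, no massage effect, and total outcome SD 1 at prevalence 50%. A factor of effect b then accounts for b² × 0.25 of the variance, which is 0.0625 for b = 0.5 and 0.1225 for b = 0.7. With the imbalance fixed, only the rest is random. The SD of the mean difference is √((1 − 0.25b²) × 2/30), which is 0.250 or 0.242. The t-test's own standard error still includes the factor's within-arm variance and is about 0.258, so its cut-off is about 1.96 × 0.258 = 0.506.
- b = 0.5: P(Z > (0.506 − 0.10)/0.250) + P(Z > (0.506 + 0.10)/0.250) = 0.052 + 0.008 = 6.0%.
- b = 0.7: P(Z > (0.506 − 0.14)/0.242) + P(Z > (0.506 + 0.14)/0.242) = 0.065 + 0.004 = 6.9%.

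Simulating the actual t-test (400,000 trials per setting) gives 5.9% and 6.8%. At exact balance (15 versus 15) it gives 4.3% and 3.6%, so the test is then conservative. Averaged over random allocations the rate is 5.0-5.1%.

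**Power with three covariates.** Variance ratio = (1 − R²) × 57/(57 − 3), with 55 residual degrees of freedom, at d = 0.736. R² is assumed.

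| R² | Variance ratio | Power |
|---|---|---|
| 0 | 1.056 | 77.8% |
| 0.05 | 1.003 | 79.8% |
| 0.10 | 0.950 | 81.9% |
| 0.20 | 0.844 | 86.1% |
| 0.30 | 0.739 | 90.3% |

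Break-even is R² = 1 − 54/57 = 5.3%. With seven covariate terms it rises to 1 − 50/57 = 12.3%, and power with unrelated covariates falls to 74.5%.

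**The case against.** The strongest reply is that an unadjusted t-test is valid under proper randomisation. That stands. A reader might infer that omitting adjustment inflates the trial's type I error, but this does not follow. The 6-7% applies only once a 20-point imbalance in a fairly strong factor has occurred, it is offset by rates below 5% when the arms are balanced, and the average is about 5%.

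Second, the main weakness of this design is predictable allocation by a researcher who knows the groups, and adjustment does not cure it. That also stands. A model removes the measured part of an imbalance and leaves selection on unmeasured features untouched. The imbalance figures above assume ideal randomisation; the documents give no basis for a figure under odd/even allocation.

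Third, it is tempting to say that the SAP itself regards these factors as predictive. It only labels them independent variables, and since allocated group is missing from the list, the label may be loose. The Protocol's Background does say "Psychological factors include fear and anxiety, previous experiences, inadequate support, inadequate knowledge", but age, education and willingness to become pregnant are not in that list of causes. Only the optional information item comes close.

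Fourth, the precision gain is not established. No R² is given, and no VAS or STAI is planned before massage, so the covariates likely to be most prognostic are unavailable. Entry criteria (first labour, age 19-40, 38-42 weeks, spontaneous onset) already narrow some variation.

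Fifth, the text is in the past tense. If outcomes have been seen, a covariate list can no longer be fixed in advance.

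What survives is that the plan names these variables, collects at least three of them, and has no analysis that uses them for the massage comparison.

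**Conclusion.** The point holds as a gap in the analysis plan, not as an error that invalidates the planned test. The massage effect on pain, phase duration and anxiety is never estimated with the SAP's own background factors held equal, although three of those factors are documented on the Questionnaire Form.

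The size is moderate. A given 40-50% prevalent factor has about a 15% chance of a 20-point imbalance, with a shift of 0.10-0.14 SD if it occurs. Adjustment changes power by anything from a loss of about 2 points to a gain of about 10. These results rest on an assumed factor effect of 0.5-0.7 SD, an assumed R² of 0-30%, a two-sided test, and a detectable difference solved backwards from 30 per arm. The absence of any adjusted analysis rests on the text alone.

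**What to change.** In the SAP section Data analysis, add a linear model for each VAS score, the STAI score and each phase duration. Include allocated group, age (continuous), educational status (two levels, with the cut-point stated in advance) and willingness to become pregnant. Collecting information about labour may be added as a fourth covariate; if unrelated to the outcome, four covariates would bring power to about 77% instead of 78%. Keep the list whatever the baseline p-values show, and do not enter all seven factors with 60 women. Report the adjusted mean difference with its 95% CI beside the unadjusted t-test. State what the independent variables are for, and name allocated group among them.

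The adjusted estimate can be the main result only if the model is fixed before outcome data are seen. Otherwise label it a post hoc sensitivity analysis. Either way, state that it does not deal with selection through predictable allocation.

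The cost is SAP wording and one regression per outcome on data already collected, seven in all (three VAS, one STAI, three durations). No extra women, visits or staff are needed. The price is three or four degrees of freedom, or about 2-3 points of power if the covariates prove unrelated to the outcome.
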